4 STUDY DESIGN

4.1 OVERALL DESIGN

The design for this study is a pilot, randomized, double-blind, sham-controlled clinical trial which will be used to investigate the effects of alpha-tACS on patients with systemic lupus erythematosus (SLE), as well as determine the relationship between physiological changes and clinical changes. We are recruiting from a clinical population. For this trial, we are seeking up to 72 males and non-pregnant females, ages 18-65, with a diagnosis of SLE, free of benzodiazepines and anticonvulsant medication, and at a low risk for suicide according to the Hamilton Depression Rating Scale (HDRS17). We anticipate having evaluable data from at least 45 participants. All women of child-bearing potential will be asked to take a pregnancy test during the initial session in order to determine eligibility for the study; nursing or pregnant participants will be excluded from participation and all women of child-bearing potential will be required to use an appropriate form of birth control throughout their participation. These individuals will be outpatients and may seek mental health care from a family practitioner, therapist or psychiatrist.

This is a single-site, pilot clinical trial with 3 arms of equal allocation (1:1:1). We estimate 2 years to complete study enrollment. Participants will be randomly assigned to one of three arms; active sham stimulation, individualized alpha-tACS (usually 8-12Hz), or individualized theta-tACS (alpha frequency minus 4 Hz). Active sham stimulation will include 20 seconds of ramp-in to 40 seconds of 10 Hz tACS with a ramp out of 20 seconds for a total of 80 seconds of stimulation. The choice of an active sham is motivated to enhance success of patient blinding by mimicking skin sensations associated with tACS. Alpha- tACS and theta-tACS will have a 20 second ramp-in and ramp-out with 40 minutes of stimulation for a total of 2440 seconds of stimulation. Stimulation waveform is a sine-wave with an amplitude of 1 mA. In each arm, participants will stay in a relaxed and yet controlled state by watching a nature movie such as “Reefscape” during stimulation.

Eligible participants who complete this clinical trial will have a total of 9-11 visits; including an initial screening session, 5 days of stimulation, a visit for a structural MRI, a 2 and a 4 week follow up visit (follow up sessions are measured from end of stimulation). Participants will also be asked to complete self-report surveys via REDCap at a 3-month time point measured from completion of the intervention. The initial session will take approximately 3 hours, each blood draw will take 30 minutes (and will be included in other visits when possible), the first and last day of stimulation will take approximately 5 hours. Days 2 through 4 of stimulation will take 2 hours each day. The visit for the structural MRI takes approximately 45 minutes. The 2-week follow up will take approximately 3 hours and the 4-week follow up will take approximately 4 hours. The 3-month surveys will take approximately an hour. We estimate that total participation to be approximately 28 hours.

If a participant is unable to complete his/her blood draws during the indicated sessions, there may be an additional 2 sessions.

Lupus Brain Protocol		Version 1.8 4 March 2022
-------------------------	--	-----------------------------

As this study requires several days of participation in a row, we will allow participants to miss one stimulation session, as long as it is made up at the end of the stimulation week. In addition, follow-up sessions will be permitted to be scheduled \pm 3 days to account for possible scheduling problems.

Our primary objective is to investigate the physiological changes in patients with SLE over the course of a 5-day, 40-minute stimulation protocol, specifically changes in alpha oscillation power from resting state EEG recordings over the course of the intervention (Day 1 to Day 5 of stimulation). As a secondary objective, we are looking to elucidate the relationship between changes in EEG and changes in clinical assays.

In the light of COVID-19, we will offer participants the option to consent and conduct patient self-reported questionnaires and patient assessments remotely to protect our high-risk patient population. This option will continue throughout the remainder of the study. Self-reported questionnaires and SLE indices detailed in the schedule of activities will be done using REDCap's secure survey function. All study staff has been vaccinated against COVID-19.

Patient assessments will be conducted using a UNC approved virtual platform. Participants will meet with the study coordinator on the phone or through a UNC approved video platform to conduct the following assessments: MINI, HDRS17, HAM-A, C-SSRS, Suicide Assessment, and YMRS. Sessions will be recorded only using audio and stored on a password protected computer until we are able to score and validate the assessments. All optional remote procedures have been noted in the schedule of assessments.

4.2 SCIENTIFIC RATIONALE FOR STUDY DESIGN

This study is a double-blind, randomized, sham-controlled interventional study. The choice of double-blind and randomized for this study is important for the integrity of our data, especially for the clinical assessments. All individuals involved with data collection (as well as all randomized participants) will not know participant assignment until all data has been collected. This will reduce implicit and explicit bias in the data collection process.

In this study, participants will be randomized in to one of three arms: active sham/placebo stimulation, individualized alpha-tACS (usually 8-12Hz), or individualized theta-tACS (alpha frequency minus 4 Hz). We propose that alpha-tACS will be the therapeutic frequency, based on work in our lab demonstrating the effect of 10Hz-tACS on depression (Alexander et al., 2019) and chronic pain (Ahn et al., 2019); whereas, previous work from our lab demonstrates that alpha oscillations exist in an antagonistic relationship with theta oscillations (Stitt et al., 2018). Therefore, theta-tACS was chosen as a control stimulation frequency for this study.

In this design, our sham/placebo stimulation is active, including 80 seconds of stimulation (20 seconds ramp-in to 40 seconds of 10 Hz tACS at 1 mA with 20 seconds of ramp-out). This choice of active sham/placebo is important to mimic the skin sensations and other transient side effects associated with stimulation. Typically, stimulation side effects only last approximately a minute into stimulation; indicating that theoretically sham/placebo stimulation should be difficult to differentiate from verum tACS.

4.3 JUSTIFICATION FOR DOSE

In a previous study at the Carolina Center for Neurostimulation, we utilized a 5-day, 40-minute stimulation paradigm to treat the mood symptoms of patients with major depressive disorder (MDD) (Alexander et al., 2019). In this study, we found that 10Hz-tACS selectively modulated alpha power as measured by changes in resting state EEG, which resulted in changes in clinical outcomes. As we are looking for long-term changes similar to this previous study, we are choosing to follow the same protocol in patients with SLE.

4.4 END OF STUDY DEFINITION

The end of this study is defined as when the last participant completes the 3 month follow up survey. In this case, we anticipate having evaluable data from at least 45 participants; therefore, enrollment will discontinue when 45 participants have completed the entire study duration including the 3-month follow up.

5 STUDY POPULATION

5.1 INCLUSION CRITERIA

- Ages 18-65 years
- Meet the 2012 Systemic Lupus International Collaborating Clinics criteria OR the 1997 American College of Rheumatology criteria for SLE diagnosis, including testing positive ANA and/or anti-dsDNA and/or anti-ENA
- Low suicide risk (score of <3 on the Suicide Item on the HDRS17)
- Capacity to understand all relevant risks and potential benefits of the study (informed consent)
- Not experiencing manic episode; a manic episode is defined as a score > 12 on the YMRS.
- Stable on all SLE-related and psychiatric meds for 4 weeks prior to screening

5.2 EXCLUSION CRITERIA

- Drug-induced SLE and any other rheumatologic or autoimmune disease (except for Sjogren's syndrome and mixed connective tissue disease)
- Positive hepatitis B surface antigen or hepatitis C antibody or HIV antibody/antigen in medical history, as patients with these illnesses cause also experience depression and cognitive impairment (from the illness itself or the treatment) that may not be mitigated by tACS, thus confounding the results.
- Have received intravenous glucocorticoids at a dosage of \geq 500mg daily within the past month
- Opportunistic infection \leq 12 weeks before initial study dosing OR currently undergoing treatment for a chronic opportunistic infection (TB, pneumocystis pneumonia, cytomegalovirus, herpes simplex virus, herpes zoster, or atypical mycobacteria)
- Acute/chronic infection requiring hospitalization \leq 30 days before screening visit AND/OR administration of parenteral (IV or IM) antibacterial, antiviral, antifungal, or anti-parasitic agents \leq 30 days before screening visit
- History of thrombophlebitis or thromboembolic disorders (e.g., blood clots) or serious adverse reactions to blood draws
- Medical illness (unstable cardiac disease, AIDS, liver or renal impairment, or malignant disease within 5 years before screening visit) or treatment of same that could interfere with study participation

- Neurological disorders, including but not limited to history of seizures (except childhood febrile seizures and ECT-induced seizures), dementia, history of stroke, Parkinson's disease, multiple sclerosis, cerebral aneurysm.
- History of moderate to severe traumatic brain injury (TBI); i.e., TBI that resulted in no or brief hospitalization, loss of consciousness of less than 20 minutes, post-traumatic amnesia of less than 24 hours, and no continuing side effects of the TBI (e.g., seizures, cognitive impairment, headaches)
- Frequent (more than once a week) or severe (requiring a visit to urgent care, hospital, or ED) migraines in the past 30 days before the screening visit
- DSM-V diagnosis of alcohol or substance abuse (other than nicotine) within the last month or a DSM-IV diagnosis of alcohol or substance dependence (other than nicotine) within the last 6 months
- Prior or current diagnosis of bipolar disorder, manic episodes, hypomanic episodes, or mixed episodes
- Prior or current diagnosis of a psychotic disorder
- Current use of benzodiazepines or anti-epileptic drugs
- Prior brain surgery
- Any brain devices/implants, including cochlear implants and aneurysm clips or other factors that are contraindicated for undergoing an MRI
- Non-English speakers
- Pregnancy, nursing, or if female and fertile, unwilling to use appropriate birth control measures during study participation
- Concurrent medical condition or treatment for a medical disorder that, in the opinion of the investigator, could confound interpretation of results or affect the patient's ability to fully participate in the study.
- Anything that, in the opinion of the investigator, would place the participant at increased risk or preclude the participant's full compliance with or completion of the study

5.3 LIFESTYLE CONSIDERATIONS

Benzodiazepine use will be prohibited during this study, unless used as needed. If participants are prescribed benzodiazepines as needed (PRN), they will be requested not to use benzodiazepines within 48 hours of a study session.

5.4 SCREEN FAILURES

In the design of this study, all participants will be screened by a clinician ([name]) who will determine eligibility based on diagnosis of SLE. However, this process does not necessarily account for all exclusion criteria.

In the case that a participant enrolls to participate in the trial, but does not meet criteria, the study coordinator completing the screening process will clearly explain why the participant does not meet criteria. However, in the case that a participant does not qualify based on suicide risk, procedures outlined below must be followed to ensure participant safety.

After obtaining participant informed consent, the HDRS will be administered, which contains a question related to suicidal thoughts/actions. If someone answers greater than 2 (i.e., either "suicidal ideas or gesture" or "attempts at suicide"), their participation in the study will be immediately stopped and [name] (Co-I, responsible for participant safety) will be contacted for acute assessment. In the case that they do not see anyone for their depression, [name] will assist the participant in seeking medical care.

This may include facilitating contact with the subject's psychiatrist/primary care physician in order to establish a plan for safety, continued care, and follow-up. If the patient does not have an established provider, [name] will assist the patient in establishing care. If at any point in the assessment, the patient is deemed to be an imminent risk of harm to self or others, study personnel will enlist the aid of campus security to ensure that the patient is safely escorted to the Emergency Department for further care.

[name] will review sMRIs for incidental findings of malignancy prior to randomization and tACS stimulation. In cases of incidental findings, the patient will be disqualified from the study and the study team will follow [name] recommendations regarding facilitating contact with appropriate providers for medical care. If a patient has received a clinical or research MRI in the 3 months before screening and had been found to have no evidence of malignancy, then they would not need to undergo an MRI for this study given there has been no change in clinical status or symptoms during that time.

5.5 STRATEGIES FOR RECRUITMENT AND RETENTION

This clinical trial will utilize multiple recruitment strategies in order to communicate this opportunity to as many potential participants as possible, including posting ads in the local newspapers, including the Independent Weekly (free). In addition to newspapers we will have postings on websites such as ClinicalTrials.gov. We will have contact information and a brief summary of the clinical trial posted on the Carolina Center for Neurostimulation website, Thurston Arthritis Research Center Website, and on the [name] Lab Twitter page. These strategies will assist in recruiting patients. Finally, in addition to

these recruitment strategies, we will have information about our study with study coordinator contact information on Join the Conquest, ClinicalTrials.gov. Interested individuals need simply to read the information about the study and contact the study coordinator to complete the phone screening.

Furthermore, [name], principal investigator, is an expert in SLE and will be able to identify potential candidates and provide materials for those interested in enrolling among the patients seen at the UNC Rheumatology Specialty Clinic.

Our retention strategy includes a payment schedule of four times per participant. The participant will receive payment at the initial session, Days 1 through 5 of stimulation, both follow up sessions, and the final 3-month follow up. The research staff will also give each participant a reminder call for the initial session, the MRI visit, the first day of stimulation, and each follow up session. Each research staff member will be easily available for the participants to contact via email or phone. The inclusion criteria state that each participant must be able to understand all risks and benefits associated with this study. We will be asking each participant to answer questions about the consent form to determine that the study process and the duration of participation are completely understood by all participants. We will aim to have a specific research team member assigned to complete all sessions with the same participant. However we will not require the same researcher to be present during stimulation sessions 2 through 4. The study team will work hard at forming rapport with the participant so they feel comfortable and willing to discuss what may be sensitive information. Retention will be quantified by the fraction of participants coming to each scheduled session (the data from each session will be scored and documented the day of the session).

As this study requires several days of participation in a row, we will allow participants to miss one stimulation session, as long as it is made up at the end of the stimulation week. If two consecutive stimulation sessions are missed, the participant will be withdrawn from participation. This schedule would permit the participant to still receive the full intervention (5 days of stimulation) without being withdrawn from the study due to unforeseen circumstances (e.g., inclement weather, car trouble). In addition, follow-up sessions will be permitted to be scheduled \pm 3 days to account for possible scheduling problems; this would permit the two-week follow-up to occur 11-17 days after completion of the intervention and the four-week follow-up to occur 25-31 days after completion of the intervention.

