7 STUDY INTERVENTION DISCONTINUATION AND PARTICIPANT DISCONTINUATION/WITHDRAWAL

7.1 DISCONTINUATION OF STUDY INTERVENTION

Discontinuation from the week of stimulation does not mean discontinuation from the study, and remaining study procedures should be completed as indicated by the study protocol. If a clinically significant finding is identified (including, but not limited to changes from baseline) after enrollment, the investigator or qualified designee will determine if any change in participant management is needed. Any new clinically relevant finding will be reported as an adverse event (AE).

The study intervention (i.e., the 5 consecutive days of stimulation) will be discontinued for the following reasons:

- A participant develops increased suicidal risk, as determined by an acute assessment by [name].
- A participant has a YMRS score greater than to 12.
- The participant misses two consecutive days of stimulation.
- The participant misses a single day of stimulation and is unable to make it up at the end of the stimulation week.
- Any clinical adverse event (AE), laboratory abnormality, intercurrent illness or other medical condition, or situation occurs such that continued participation in the study would not be in the best interest of the participant.
- The participant meets any exclusion criteria (either newly developed or not previously recognized).
- A participant wishes to withdraw from further participation for any reason.

If the participant withdraws from the intervention, he/she will be followed through the 4 week follow-up with the designated clinical assessments to ensure participant safety:

- HDRS
- YMRS
- Suicide Questionnaire

Additional measures may be continued if deemed appropriate (e.g., EEG, cognitive tasks, Comparative Pain Scale, Pain Catastrophizing Scale).

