7.2 PARTICIPANT DISCONTINUATION/WITHDRAWAL FROM THE STUDY

A study participant will be discontinued from further participation if:

- Any clinical adverse event (AE), serious adverse event (SAE), laboratory abnormality, intercurrent illness or other medical condition, or situation occurs such that continued participation in the study would not be in the best interest of the participant.
- The participant meets any exclusion criteria (either newly developed or not previously recognized).
- A participant wishes to withdraw from further participation for any reason.

The reason for participant discontinuation or withdrawal from the study will be recorded with the participant files. Participants who sign the informed consent form and are not randomized will be replaced. Participants who sign the informed consent form, and are randomized and receive the full study intervention (5 consecutive days of 40 minutes of stimulation), and subsequently withdraw or are withdrawn or discontinue from the study will not be replaced. However, participants who sign the informed consent form, and are randomized and receive only part of the study intervention, and subsequently withdraw or are withdrawn or discontinue from the study will be replaced.

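### Sections 5.5 and 7.1 give different consequences for missing two consecutive stimulation sessions, so 2-week and 4-week safety follow-up could be omitted

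*Combined protocol and SAP*

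**What the plan says.** Section 5.5 allows one missed stimulation session if it is made up at the end of the week. It then sets the limit: "If two consecutive stimulation sessions are missed, the participant will be withdrawn from participation". The next sentence explains that the make-up allowance lets a participant receive all five days "without being withdrawn from the study due to unforeseen circumstances (e.g., inclement weather, car trouble").

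Section 7.1 deals with stopping the intervention. It opens: "Discontinuation from the week of stimulation does not mean discontinuation from the study, and remaining study procedures should be completed". One of its listed reasons is "The participant misses two consecutive days of stimulation". For a participant who stops the intervention, it says that "he/she will be followed through the 4 week follow-up with the designated clinical assessments to ensure participant safety", and names the HDRS, the YMRS and the suicide questionnaire. For EEG, cognitive tasks and the two pain scales it says: "Additional measures may be continued if deemed appropriate".

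Section 7.2 deals with leaving the study. It begins "A study participant will be discontinued from further participation if" and gives three reasons: an adverse event or other medical situation, meeting an exclusion criterion, and the participant's own wish. Missed sessions are not among them.

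**The concern.** One event has two stated consequences in operative text. Under 5.5 the participant leaves the study. Under 7.1 stimulation stops and the participant stays.

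Safety follow-up is the main thing at stake. Section 7.1 continues assessments after stopping for the participant's safety, and Section 2.3.1 acknowledges that theta-tACS could in theory worsen depression. A coordinator working from 5.5 would have no instruction to hold the 2-week and 4-week visits. The 2-week visit matters for a further reason. Section 7.4.2 counts an event as a TEAE only if it lasts 14 days or more, and gives persistence at the 2-week follow-up as the illustration. Without that visit, an event that should count toward the TEAE stopping rule could go unrecorded.

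Two operational rules also depend on study status: replacement of partly treated participants (7.2) and reassignment of randomization codes (6.2.1).

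**Working it through.** The point is textual, so the sections are set side by side first. The arithmetic only bounds the size.

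**1. Is it the same event?** Section 6.1.2 provides one stimulation session per day. Two consecutive sessions (5.5) and two consecutive days (7.1) are therefore the same trigger.

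**2. What follows from it?**

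| Question | Section 5.5 read literally | Section 7.1 |
|---|---|---|
| Stimulation | Ends | Ends |
| Study status | Withdrawn; next sentence refers to the study | Remains in the study |
| HDRS, YMRS, suicide questionnaire to week 4 | Not mentioned | Continued |
| EEG, cognitive tasks, pain scales | Not mentioned | Opening sentence expects remaining procedures; later list makes these discretionary |

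Section 7.2 agrees with 7.1 by omission. The last row of the table shows a second, smaller conflict, which lies inside 7.1 itself.

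**3. Replacement and code reuse.** Section 7.2 replaces a participant who received part of the intervention and then withdraws, is withdrawn or discontinues from the study. Section 6.2.1 reassigns the code of anyone who withdraws, is withdrawn or is lost to follow-up. A participant withdrawn under 5.5 meets both conditions. One who remains in the study under 7.1 does not clearly meet either.

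**4. How many participants?** The documents give no rate of missed sessions. Take 72 randomized (Section 1.2.1) and assume a range of 2% to 20%:

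- 72 × 0.02 = 1.44, about 1 participant
- 72 × 0.05 = 3.6, about 4
- 72 × 0.10 = 7.2, about 7
- 72 × 0.20 = 14.4, about 14

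The only related figure in the plan is the gap between 72 and the 45 evaluable: 72 − 45 = 27, and 27/72 = 37.5%. It is no more than a ceiling, because it covers every reason for being non-evaluable.

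**5. Is the planned primary analysis affected?** Section 9.3 analyses only those who complete all five days, so these participants are excluded under either rule. The plan's power statement (Section 9.2: difference about 2, SD about 1.2, 20 per group, alpha 0.05, more than 80%) can be reproduced. Sidedness is not stated, so two-sided is assumed.

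- Standardized difference: 2/1.2 = 1.667
- 20 per group: noncentrality 1.667 × √(20/2) = 5.27, power 0.9993 (t test)
- 15 per group (45/3): noncentrality 1.667 × √(15/2) = 4.56, power 0.993

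The stated power holds on the plan's own inputs, and it does not depend on which section is applied.

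**The case against.** The best defence is that the protocol uses its withdrawal wording loosely, and that Section 7, not a recruitment and retention section, governs discontinuation. Section 9.3 refers back to Section 7. Within 7.1, a wish to withdraw from further participation is itself a reason to stop the intervention, followed by safety assessments to week 4. Section 8.3.6 ends participation on pregnancy and still continues the same follow-up. Section 8.3.4 separately requires adverse events to be recorded until after the 3-month follow-up and followed to resolution. On this reading, 5.5 would not end safety follow-up.

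Part of this stands: loss of safety data is possible, not established. But 8.3.6 states its continued follow-up expressly, whereas 5.5 does not, and the next sentence of 5.5 names the study. No section says which one prevails.

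A reader might infer several stronger points that the documents do not support:

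- **That up to 27 participants (37.5%) would be affected.** That gap also includes suicidality, YMRS scores, adverse events, voluntary withdrawal and loss to follow-up. Section 4.4 counts toward 45 only those who complete the 3-month follow-up, so some people with all five sessions could fall in the gap. The synopsis describes 72 as a recruitment figure, so it may also include screen failures.
- **That all EEG would be lost.** Anyone who attended Day 1 should already have EEG from before and after stimulation (6.1.2, 8.1.1). Later EEG may be missing under 7.1 as well.
- **That non-completers could no longer be compared by arm.** Their number, reasons and baseline data by arm need no later visit. Only a comparison of their later outcomes would suffer. Section 9.4.1 promises sensitivity analyses in general terms, but none is specified for these participants.

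**Conclusion.** The contradiction holds. Two consecutive missed sessions lead to study withdrawal in 5.5 and to stopping stimulation only in 7.1, and 7.2 does not list the event. The likely harm is omitted 2-week and 4-week safety assessments for those affected, with a possible undercount of TEAEs, and inconsistent handling of replacement and code reuse.

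The size is unknown. The figure of about 1 to 14 participants rests wholly on an assumed rate of 2% to 20% of 72. Actual loss further depends on staff applying 5.5 literally. The planned primary result and its power are not affected. This is an inconsistency to correct for the sake of safety follow-up, not a flaw in the primary analysis. The documents do not settle which rule was intended, and this review takes no position on that.

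**What to change.** Reconcile Sections 5.5, 7.1 and 7.2 so that missing two consecutive sessions has one stated consequence for each of four things: study status, safety follow-up, replacement, and reuse of the code under 6.2.1. The sponsor decides which rule applies.

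In the same amendment, reconcile the opening sentence of 7.1, which expects remaining procedures to be completed, with its later list that makes EEG and other measures discretionary. Resolving the conflict does not require EEG to be made compulsory. A participant stopped after two missed sessions may have no Day 5 visit at which to record it.

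The cost is a wording amendment with IRB review and a short notice to staff. Extra recordings would arise only if the sponsor decides that EEG is expected after stimulation stops.
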